## **5.0 Investigational Plan**

### **5.1 Overall Study Design and Plan: Description**

This is a Phase 2, multicenter, OLE study to assess the long-term safety, tolerability, and efficacy of upadacitinib in RA subjects who have completed Study M13-550 or Study M13-537 Phase 2 RCT with upadacitinib. This study is designed to enroll up to 500 subjects. Subjects will be treated for approximately 312 weeks.

Only those subjects who have met all of the specified inclusion criteria and none of the exclusion criteria will have an option to enter into the OLE study to receive upadacitinib, as long as the subject is willing and the Investigator believes that continuing therapy with upadacitinib is appropriate.

All eligible subjects will be assigned to upadacitinib 6 mg BID immediately after or up to 30 days following the Last Visit (Week 12) of Study M13-550 or Study M13-537 Phase 2 RCT.

Subjects who are unable to tolerate 6 mg BID will be discontinued from the study.

At Week 6, if a subject fails to achieve at least 20% improvement from RCT Baseline in both Tender Joint Count (TJC) and Swollen Joint Count (SJC), upadacitinib dose should be increased to 12 mg BID as long as the Investigator has no safety concerns. After 6 weeks of treatment with upadacitinib 12 mg BID, the improvement in TJC and SJC will be re-assessed at next scheduled visit (Week 12).

If the subject on 12 mg BID fails to achieve at least 20% improvement in both TJC and SJC from RCT Baseline the subject will be discontinued.

At Week 12, the same process will be followed. If a subject still on 6 mg BID fails to achieve at least 20% improvement from RCT Baseline in both TJC and SJC, upadacitinib dose should be increased to 12 mg BID. The improvement in both TJC and SJC will be re-assessed after 6 weeks of treatment with 12 mg BID at Week 18 (an optional study visit).

Subjects who fail to achieve at least 20% improvement from RCT Baseline in both TJC and SJC with 12 mg BID at Week 18 will be discontinued.

After Week 12, if a subject fails to show at least 20% improvement from RCT Baseline in both TJC and SJC at 2 consecutive scheduled study visits, the subject will be discontinued.

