Starting at Week 6 and during any scheduled or unscheduled visits thereafter, upadacitinib dose may be increased from 6 mg BID to 12 mg BID (or 30 mg QD from January 2017, see below) if a subject fails to achieve Low Disease Activity (LDA) status (defined by CDAI > 10) and has no safety concerns per Investigator's judgment.

At any visit, upadacitinib dose may be decreased back to 6 mg BID (or 15 mg QD from January 2017) per Investigator's judgment if there are safety and/or tolerability concerns, due to an adverse event or reaching one of the protocol specific toxicity management thresholds. Dose increase back to 12 mg BID (or 30 mg QD from January 2017) is not allowed.

From January 2017, all subjects who are at Week 72 or beyond will receive a once-daily tablet formulation. Subjects who are on 6 mg BID capsule dosing will be transitioned to 15 mg QD tablet dosing. Subjects who are on 12 mg BID capsule dosing will be transitioned to 30 mg QD tablet dosing. The capsule formulation will not be available to subjects once the transition to tablet formulation has occurred.

[figure not shown]
Starting with Amendment 5, subjects who are receiving 30 mg QD open-label upadacitinib will have the option to decrease the dose to 15 mg QD based on investigator's discretion.

The change to once daily tablet formulation in this study is based on extrapolation of pre-clinical efficacy models and analyses of PK, pharmacodynamic, safety, and efficacy data from the Phase 1 studies in healthy volunteers (single and multiple ascending dose Studies M13-401 and M13-845, respectively) and completed Phase 2b randomized, controlled studies (RCTs) in RA subjects (Studies M13-537 and M13-550). The doses

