### **5.5.3 Selection and Timing of Dose for Each Subject**

Subjects should take study drug as outlined in Section [5.5.1](#).

On scheduled study visit days, subject should follow their regular routine for study drug administration.

Each subject's dosing schedule should be closely monitored by the site at each study visit by careful review of the subject's dosing diary ([Appendix K](#)).

Capsule Formulation:

If a subject should forget to take his/her study drug dose at his/her regularly scheduled dosing time, he/she should take the forgotten dose as soon as he/she remembers the dose was missed as long as it is at least 6 hours before his/her next scheduled dose. If a subject only remembers the missed dose within 6 hours before next scheduled dose, the subject should skip the missed dose and take the next dose at the scheduled time.

Tablet Formulation:

If a subject should forget to take his/her study drug dose at his/her regularly scheduled dosing time, he/she should take the forgotten dose as soon as he/she remembers the dose was missed as long as it is at least 10 hours before their next scheduled dose. If a subject

only remembers the missed dose within 10 hours before next scheduled dose, the subject should skip the missed dose and take the next dose at the scheduled time.

If the subject experiences a study drug interruption > 30 days, they should notify their investigator, and the investigator will determine if study drug should be restarted or if the subject should be discontinued from the study.

Subjects who, in the opinion of the Investigator, develop adverse events that require study drug interruption and/or reach protocol specified toxicity management thresholds can have the study drug interrupted for up to 30 days while recovering from the adverse event.

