### **6.2 Medical Complaints**

The investigator will monitor each subject for clinical and laboratory evidence of adverse events on a routine basis throughout the study. The investigator will assess and record

any adverse event in detail including the date of onset, event diagnosis (if known) or sign/symptom, severity, time course (end date, ongoing, intermittent), relationship of the adverse event to study drug, and any action(s) taken. For serious adverse events considered as having "no reasonable possibility" of being associated with study drug, the investigator will provide an Other cause of the event. For adverse events to be considered intermittent, the events must be of similar nature and severity. Adverse events, whether in response to a query, observed by site personnel, or reported spontaneously by the subject will be recorded.

All adverse events will be followed to a satisfactory conclusion.

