At any visit, upadacitinib dose may be decreased back to 6 mg BID per Investigator's judgment due to either an adverse event or reaching one of the protocol specific toxicity management thresholds. Dose increase back to 12 mg BID (or 30 mg QD from January 2017) is not allowed.

[figure not shown]
From January 2017, all subjects who are at Week 72 or beyond will receive a once-daily tablet formulation. Subjects who are on 6 mg BID capsule dosing will be transitioned to 15 mg QD tablet dosing. Subjects who are on 12 mg BID capsule dosing will be transitioned to 30 mg QD tablet dosing. The capsule formulation will not be available to subjects once the transition to tablet formulation has occurred. The change to once daily

tablet formulation in this study is based on extrapolation of pre-clinical efficacy models and analyses of PK, pharmacodynamic, safety, and efficacy data from the Phase 1 studies in healthy volunteers (single and multiple ascending dose Studies M13-401 and M13-845, respectively) and completed Phase 2b randomized, controlled studies (RCTs) in RA subjects (Studies M13-537 and M13-550). The doses selected, 15 mg QD and 30 mg QD, are expected to approximate the exposures achieved with the 6 mg BID and 12 mg BID immediate release formulations, respectively, which should be efficacious with an acceptable safety profile. Preliminary results from an ongoing relative bioavailability study demonstrated that single 15 mg and 30 mg doses of the once-daily formulation provide comparable AUC and significantly lower C_{max} than single doses of 12 mg immediate release (IR) formulation (AUC equivalent to 6 mg BID dose tested in Phase 2) and 24 mg IR formulation (AUC equivalent to 12 mg BID dose tested in Phase 2), respectively, under fasting conditions. At steady-state, the once-daily dose of 15 mg QD is predicted to achieve comparable daily AUC and C_{max} , and non-inferior C_{trough} to 6 mg BID IR formulation. In the Phase 2 RCTs, the 6 mg BID dose was shown to achieve the near maximum efficacy. The once-daily dose of 30 mg QD is predicted to achieve comparable daily AUC and C_{max} , and non-inferior C_{trough} to 12 mg BID IR formulation. In the Phase 2 RCTs, the 12 mg BID dose was clearly shown to achieve the plateau of efficacy.

Starting with Amendment 5, subjects who are receiving 30 mg QD open-label upadacitinib will have the option to decrease the dose to 15 mg QD based on investigator's discretion.

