10.2.1 Overview of Adverse Events Rates per 100 Patient-Years of Study Drug Exposure

The number and percentage of subjects experiencing TEAEs will be summarized for each exposure group in the open-label treated population for the following AE categories:

- All TEAEs
- Treatment-emergent serious adverse events (SAEs)
- Treatment-emergent severe adverse events
- TEAEs reasonably possibly related to study drug
- TEAEs of special interest
- TEAEs leading to discontinuation of study drug
- TEAE leading to death
- All death

For this calculation, 1 year will be considered to be 365.25 days. For each exposure group, the numerator of the overall rate will be the total number of TEAEs reported for

the event; that is, a subject can contribute more than one event to the numerator. For each treatment group, the denominator of the rates will be the total number of days exposed to study drug summed across all treated subjects divided by 365.25. Please refer to Section 8.1 for the calculation of study drug exposure. The AE rate per 100 patient-years of exposure will be calculated as $(\text{[numerator/denominator]}) * 100$. The number of AEs reported (numerator), the total number of years of study drug exposure (denominator), and the AE rate per 100 patient-years will be presented for each exposure group.

In the AE overview summary, any event with an unknown severity will be considered as severe and any AE with an unknown relationship will be considered as having "reasonable possibility" of being related to study drug.

Additional AEs may be considered for tabulation/summary based on recommendations from Clinical and Safety as deemed appropriate.

10.2.2 Adverse Events Rates per 100 Patient-Years of Study Drug Exposure by System Organ Class and Preferred Term

the TEAE rate per 100 patient-years of exposure will be tabulated by SOC and MedDRA PT for each exposure group in the open-label treated population. The SOCs will be presented in alphabetical order, and the PTs will be presented in alphabetical order within each SOC.

The following summaries of adverse events will be generated:

- All TEAEs
- Treatment-emergent serious adverse events (SAEs)
- Treatment-emergent severe adverse events
- TEAEs reasonably possibly related to study drug
- Frequent TEAEs (reported at ≥ 2 E/100PY in any exposure group)
- TEAEs leading to discontinuation of study drug
- TEAE leading to death

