10.2.3 Serious Adverse Events (Including Deaths) and Adverse Events Leading to Study Drug Discontinuation Rates per 100 Patient-Years of Study Drug Exposure

All serious adverse events (SAEs), deaths, and adverse events leading to discontinuation of study drug will be summarized by SOC and PT or each exposure group.

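### AE-discontinuation rates are not directly comparable between exposure groups 1 and 2, because AEs handled by dose reduction are not tabulated

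*SAP*

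**What the plan says.** **Dose rules.** For the lower dose, Protocol 5.1 states: "Subjects who are unable to tolerate 6 mg BID will be discontinued from the study". For the higher dose, the same section states: "At any visit, upadacitinib dose may be decreased back to 6 mg BID (or 15 mg QD from January 2017) per Investigator's judgment", where there are safety or tolerability concerns. SAP 4.2 repeats the step-down rule, with reductions "due to either an adverse event or reaching one of the protocol specific toxicity management thresholds". From Amendment 5, Protocol 5.1 also lets a subject on 30 mg QD move to 15 mg QD at the investigator's discretion, with no AE required. On either dose, Protocol 5.5.3 provides that subjects with AEs requiring it "can have the study drug interrupted for up to 30 days while recovering from the adverse event".

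**Exposure groups.** SAP 8.1 defines group 1 (6 mg BID/15 mg QD before any up-titration), group 2 (12 mg BID/30 mg QD, censored at down-titration), group 3 (6 mg BID/15 mg QD after down-titration) and group 4 (any upadacitinib). SAP 10.1 presents TEAE rates per 100 patient-years by these groups.

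**AE categories.** SAP 10.2.1 and 10.2.2 list "TEAEs leading to discontinuation of study drug" among their categories. SAP 10.2.3 adds that "adverse events leading to discontinuation of study drug will be summarized by SOC and PT" by exposure group, and 10.2.6 provides the listings. None of these sections has a category for AEs leading to dose reduction or interruption. Protocol 8.1.6.2.1 has the same gap.

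**Data collected.** Under Protocol 6.2 the investigator records, among other items, the "relationship of the adverse event to study drug, and any action(s) taken".

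**The concern.** Tolerability is part of the primary objective (Protocol 4.0, SAP 4.1). A reader who wants to know how often an AE limited treatment on each dose will look at the AE-discontinuation rows for groups 1 and 2.

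Those rows apply one counting rule to two groups with different clinical options. A subject who cannot tolerate the lower dose has no lower step, so the event ends in discontinuation and is counted. A subject who cannot tolerate the higher dose may step down and stay on study drug, so the event is not counted. With equal true intolerance on both doses, the group 2 row would then read lower. A real excess on the higher dose could appear smaller in that row, or not appear at all.

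Group 3 does not fill the gap. It shows that subjects stepped down but not why, and since Amendment 5 it mixes AE-driven with discretionary reductions.

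**Working it through.** The documents give no rate, event count or expected share on this point, so there is no figure of the plan to reproduce. The check has two parts.

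**1. Following one treatment-limiting AE through the rules**

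| Step | On 6 mg BID/15 mg QD (group 1) | On 12 mg BID/30 mg QD (group 2) |
|---|---|---|
| Interruption up to 30 days (Protocol 5.5.3) | Available; not tabulated | Available; not tabulated |
| Dose reduction (Protocol 5.1) | Not available | Available; not tabulated |
| Discontinuation (Protocol 5.1, 5.4.1) | Available; tabulated | Available; tabulated |
| End of the group's exposure (SAP 8.1) | Discontinuation or up-titration | Discontinuation or down-titration |

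The only difference in exits is the dose-reduction row. A subject who steps down for an AE leaves the group 2 denominator without adding to the group 2 discontinuation count. If that subject later discontinues, this happens outside group 2 exposure. SAP 10.2 has no explicit rule for assigning an event to a group when onset and action fall on either side of a titration.

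**2. Illustration of size**

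Inputs, all assumed:
- λ₁ = 4 per 100 patient-years, the rate of treatment-limiting AEs on the lower dose. The ratios below do not depend on it.
- R = true ratio of that rate, higher to lower dose.
- f = share of treatment-limiting AEs on the higher dose handled by reduction, from 25% to 75%.
- Treatment-limiting means an event that would end in discontinuation if no reduction were possible.

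Formulas: apparent group 2 rate = λ₁ × R × (1 − f); apparent ratio = R × (1 − f).

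| True ratio R | f = 25% | f = 50% | f = 75% |
|---|---|---|---|
| 1.0 | 4 × 0.75 = 3.0; ratio 0.75 | 4 × 0.50 = 2.0; ratio 0.50 | 4 × 0.25 = 1.0; ratio 0.25 |
| 1.5 | 6 × 0.75 = 4.5; ratio 1.125 | 6 × 0.50 = 3.0; ratio 0.75 | 6 × 0.25 = 1.5; ratio 0.375 |
| 2.0 | 8 × 0.75 = 6.0; ratio 1.5 | 8 × 0.50 = 4.0; ratio 1.0 | 8 × 0.25 = 2.0; ratio 0.5 |

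The two doses look equal in this row when R = 1/(1 − f), that is 1.33, 2.0 or 4.0 for the three values of f.

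**What a combined row would do.** If every AE-driven reduction replaced a discontinuation, counting discontinuations and reductions together would restore the true ratio (for R = 2.0, 8 against 4 per 100 patient-years). If reductions also include milder events, at m per 100 patient-years, that would only have been interrupted on the lower dose, the combined ratio becomes (λ₁R + m)/λ₁. This is too high by m/λ₁. The combined row is therefore not unbiased either.

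**The case against.** The strongest reply is that only the discontinuation rows are affected. SAP 10.2.1, 10.2.2 and 10.2.5 also tabulate all, serious, severe, related, special-interest and fatal TEAEs by exposure group, whatever action was taken. Potentially clinically significant laboratory and vital-sign values (SAP 10.1) and liver elevations (SAP 10.3.5) are by exposure group too. An AE that prompts a reduction is not lost from these tables. This stands, and it limits the point. It does not remove it: a non-serious AE that led to a reduction looks the same there as one that changed nothing. The severe row may catch some, since the general grading row in Protocol Appendix M mentions dose reduction under grade 3, but it does not separate them.

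Second, an AE on the lower dose does not in itself force discontinuation. The rule concerns inability to tolerate 6 mg BID, and interruption is open on both doses. Several events call for stopping on either dose under Protocol 5.4.1 and 6.10, such as confirmed thrombosis, gastrointestinal perforation, active TB and most malignancies. For those, reduction is no alternative and the rows are comparable. This also stands.

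Third, no SAP section names AE discontinuation as the tolerability measure or tests one dose against another, and SAP 11.0 records that safety testing was removed as not meaningful in this population. That is correct, but rates set side by side are still read against each other.

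Fourth, SAP 10.2.1 and 10.2.5 leave room for additional AE tabulations. That is an option, not a commitment to this table.

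**Conclusion.** The point holds for the AE-discontinuation rows and listings. Because reduction is possible only in group 2 and is not tabulated, those rows do not capture the same treatment-limiting events in groups 1 and 2. They tend to understate such events on the higher dose. The direction follows from the plan's own rules, provided that at least some AEs that would otherwise have ended treatment are handled by reduction. The size cannot be derived: the factor of 0.75 to 0.25 rests on an assumed f of 25% to 75%.

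A reader might infer that the SAP compares the doses on discontinuations alone, so that the higher dose will look better tolerated overall. The documents do not support that, given the other tables by exposure group. A reader might also take the understatement to equal the share of AEs that led to a reduction. That would require every reduction to replace a discontinuation, and nothing in the documents shows this.

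This is an inexpensive improvement to the reporting of a primary-objective item, not a flaw that undermines the safety analysis.

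**What to change.** In SAP 10.2.1, 10.2.2 and 10.2.3, with matching listings in 10.2.6, add by exposure group at AE onset:

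- (a) TEAEs leading to dose reduction, kept apart from discretionary Amendment 5 reductions;
- (b) TEAEs leading to study drug interruption;
- (c) TEAEs leading to discontinuation or dose reduction combined, shown as a supplement beside its components and not as the preferred comparison of groups 1 and 2.

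State in SAP 10.2 that these events are assigned to the dose at onset. Add a footnote to the AE-discontinuation tables that the dose-reduction option exists only in group 2.

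The cost is SAP wording and a few more table rows. Protocol 6.2 has the action taken recorded, so the data should exist. The case report form is not among the documents, so the sponsor should confirm that dose reduction and interruption are coded there. The downside is that the combined row mixes milder with more serious actions, which is why its components stay on display. No dosing rule changes.

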10.2.4 Frequent Adverse Events by System Organ Class and Preferred Term

TEAEs occurring at ≥ 2 E/100PY in any of the exposure groups will be summarized by MedDRA PT in decreasing rate.

10.2.5 Adverse Events of Special Interests Rates per 100 Patient-Years of Study Drug Exposure

The Adverse Events of Special Interests (AESI) categories will be summarized and presented for each exposure group using SOC and MedDRA PT. The AESI categories will be identified per Standard MedDRA Queries (SMQs)/Company MedDRA Queries (CMQs) in [Table 5](#) below. Adjudicated cardiovascular events will be summarized and presented by treatment groups using CAC adjudicated categories.

Table 5. AESI for Upadacitinib with SMQs/CMQs/PTs Searches

AESI	Type of MedDRA Query	Broad or Narrow Search	SMQ/CMQ Search Criteria
Serious Infections	CMQ		"Infections" – Subset for SAEs
Opportunistic Infection excluding Tuberculosis and Herpes Zoster	CMQ		"Opportunistic Infection excluding Tuberculosis and Herpes Zoster"
Possible Malignancy	SMQ	Narrow	"Malignancies"
Malignancy	SMQ		"Malignant tumours"
Non-Melanoma Skin Cancer (NMSC)	SMQ	Narrow	Skin Malignant tumours (Narrow SMQ) removing Melanoma CMQ
Malignancy excluding NMSC			"Malignant tumours" SMQ removing NMSC output
Lymphoma	SMQ		"Malignant Lymphomas"
Hepatic Disorder	SMQ	Narrow	"Drug Related Hepatic Disorders"
Adjudicated Gastrointestinal Perforations	Output from adjudication		
Anemia	CMQ		"Non-Hemolytic and Non-Aplastic Anemias"
Neutropenia	CMQ		"Hematological Toxicity – Neutropenia"
Lymphopenia	CMQ		"Hematological Toxicity – Lymphopenia"
Herpes Zoster	CMQ		"Herpes Zoster"
Creatine Phosphokinase (CPK) Elevation	PT		Search only for the PT of "Blood creatine phosphokinase increased"
Renal Dysfunction	SMQ	Narrow	"Acute Renal, Failure"
Active Tuberculosis	CMQ		"Active Tuberculosis"
Adjudicated Cardiovascular Events	Output from CAC		
MACE*			
Cardiovascular Death			
Non-fatal Myocardial Infarction			
Non-fatal Stroke			

Table 5. AESI for Upadacitinib with SMQs/CMQs/PTs Searches (Continued)

AESI	Type of MedDRA Query	Broad or Narrow Search	SMQ/CMQ Search Criteria
Undetermined/Unknown Cause of Deaths			
Other Cardiovascular events			
Adjudicated Thrombotic Events	Output From CAC		
Venous Thromboembolic Events**			
Deep Vein Thrombosis			
Pulmonary Embolism			
Other Venous Thrombosis			
Arterial Thromboembolic Events (non-cardiac, non-neurologic)			

CAC = Cardiovascular Adjudication Committee; CMQ = company MedDRA query; PT = preferred term; SMQ = standard MedDRA query

* MACE; Major Adverse Cardiovascular Events, defined as cardiovascular death, non-fatal myocardial infarction and non-fatal stroke.

** Venous thromboembolic events (VTE) include deep vein thrombosis (DVT) and pulmonary embolism (PE) (fatal and non-fatal).

Additional AEs may be considered for tabulation/summary based on recommendations from Clinical and Safety as deemed appropriate.

10.2.6 Listing of Serious Adverse Events (Including Deaths) and Adverse Events Leading to Study Drug Discontinuation

All serious adverse events (SAEs), deaths, and adverse events leading to discontinuation of study drug will be listed.

